The use of high dose chemotherapy followed by autologous peripheral blood stem cell (PBSC) transplantation in recurrent NPC has shown promise when compared with standard chemotherapy. Airoldi and colleagues⁵ reported long-term results of high dose chemotherapy as late intensification with autologous PBSC support in 6 patients. After conventional chemotherapy, there was 1 CR (16%), 3 PR (50%), and 2 NC (34%). After high dose chemotherapy, 4 patients achieved CR (66%), 1 PR (17%), and 1 MR (17%). Toxicity was manageable. After a median follow-up of 30 months (range, 14-50), two

patients were alive without disease (34%), one was alive with bone disease (16%), and three (50%) died of disease at 16, 18, and 24 months⁵.

Chen T-Y et al also reported that high dose chemotherapy followed by autologous stem cell transplantation is feasible with acceptable toxicity and can convert partial remission into complete remission⁶.

3. SPECIFIC AIMS:

- 3.1.** To evaluate the response rates for patients undergoing high dose conditioning using Etoposide, Carboplatin and Ifosfamide followed by autologous stem cell transplantation for the treatment of recurrent NPC in children, adolescents, and young adults.
- 3.2.** To evaluate the toxicities associated with undergoing high dose conditioning using Etoposide, Carboplatin and Ifosfamide followed by autologous stem cell transplantation for the treatment of recurrent NPC in children, adolescents, and young adults.

4. RESEARCH PLAN:

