5.5.6. Possible Risks

- 5.5.6.1.** Aggressive supportive care improves outcome. This study will follow the institutional supportive care guidelines for high-dose chemotherapy and stem cell transplant.
- 5.5.6.2.** The possible risks of this treatment include those associated with high-dose chemotherapy and autologous stem cell transplantation including:

1. Pancytopenia requiring transfusion support
2. Bacterial infection
3. Fungal infection
4. Nausea, vomiting
5. Loss of appetite
6. Mucositis
7. Alopecia
8. Allergic reactions to the chemotherapy agents or supportive care agents
9. Liver damage
10. Kidney damage
11. Hemorrhagic cystitis
12. Sinusoidal obstruction syndrome (SOS) of the liver
13. Engraftment syndrome
14. DMSO adverse effects during stem cell infusion

5.5.6.3. Drug specific risks are listed below:

Possible Side Effects of Carboplatin and Etoposide (Table Version Date: October 8, 2013)

COMMON, SOME MAY BE SERIOUS

In 100 people receiving Carboplatin, Etoposide, more than 20 and up to 100 may have:

- Hair loss
- Vomiting, nausea, diarrhea, loss of appetite
- Infection, especially when white blood cell count is low

COMMON, SOME MAY BE SERIOUS

In 100 people receiving Carboplatin, Etoposide, more than 20 and up to 100 may have:

- Anemia which may require blood transfusions
- Bruising, bleeding
- Belly pain
- Sores in mouth which may cause difficulty swallowing
- Tiredness
- Fever, chills

OCCASIONAL, SOME MAY BE SERIOUS

In 100 people receiving Carboplatin, Etoposide, from 4 to 20 may have:

- Constipation
- Numbness and tingling in fingers and toes
- Allergic reaction which may cause rash, low blood pressure, wheezing, shortness of breath, swelling of the face or throat
- Heart failure or heart attack which may cause chest pain, shortness of breath, swelling of ankles, and tiredness
- Severe skin rash with blisters and peeling which can involve inside of mouth and other parts of the body
- Liver damage which may cause yellowing of eyes and skin, swelling

RARE, AND SERIOUS

In 100 people receiving Carboplatin, Etoposide, 3 or fewer may have:

- Changes in vision
- Changes in taste
- Damage to organs which may cause hearing and balance problems
- Cancer of bone marrow (leukemia) caused by chemotherapy

Possible Side Effects of Filgrastim (Table Version Date: October 24, 2013)**COMMON, SOME MAY BE SERIOUS**

In 100 people receiving Filgrastim, more than 20 and up to 100 may have:

- Nausea, vomiting
- Pain in bone

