OCCASIONAL, SOME MAY BE SERIOUS

In 100 people receiving Filgrastim, from 4 to 20 may have:

- Anemia which may cause tiredness, or may require transfusion
- Damage to the lungs which may cause shortness of breath
- Internal bleeding which may cause coughing up blood
- Swelling or tenderness of vessels

RARE, AND SERIOUS

In 100 people receiving Filgrastim, 3 or fewer may have:

RARE, AND SERIOUS

In 100 people receiving Filgrastim, 3 or fewer may have:

- Rupture of the spleen leading to bleeding in the belly

Possible Side Effects of Ifosfamide (Table Version Date: May 28, 2013)**COMMON, SOME MAY BE SERIOUS**

In 100 people receiving Ifosfamide, more than 20 and up to 100 may have:

- Anemia which may require transfusion
- Nausea, vomiting
- Infection, especially when white blood cell count is low
- Blood in urine
- Hair loss

OCCASIONAL, SOME MAY BE SERIOUS

In 100 people receiving Ifosfamide, from 4 to 20 may have:

- Abnormal heartbeat
- Bruising, bleeding
- Kidney damage which may cause swelling, may require dialysis
- Fluid around lungs
- Confusion, sleepiness, disorientation
- Sterility

RARE, AND SERIOUS

In 100 people receiving Ifosfamide, 3 or fewer may have:

- Damage to the heart or heart failure which may cause tiredness, shortness of breath, or swelling of ankles

Possible Side Effects of Mesna (Table Version Date: May 28, 2013)**COMMON, SOME MAY BE SERIOUS**

In 100 people receiving Mesna, more than 20 and up to 100 may have:

- Nausea, vomiting
- Tiredness, headache
- Pain in arms, legs
- Unpleasant taste

OCCASIONAL, SOME MAY BE SERIOUS

In 100 people receiving Mesna, from 4 to 20 may have:

- Low blood pressure which may cause feeling faint

RARE, AND SERIOUS

In 100 people receiving Mesna, 3 or fewer may have:

- None

Possible Side Effects related to blood stem cell harvest and infusion

COMMON, SOME MAY BE SERIOUS

In 100 people receiving Ifosfamide, more than 20 and up to 100 may have:

- Nausea and vomiting
- Unpleasant taste and smell of agent used to preserve stem cells when frozen
- Headache
- Fever
- Discolored urine
- Tingling of the lips
- Muscle cramping

OCCASIONAL, SOME MAY BE SERIOUS

In 100 people receiving Ifosfamide, from 4 to 20 may have:

- Seizures (rare)
- Blood loss
- Infection
- Skin rash, hives
- Flushing (redness and warmth of the skin)
- Dizziness or fainting
- Chills
- Changes in heart rhythm (rare and easily treated)

RARE, AND SERIOUS

In 100 people receiving Ifosfamide, 3 or fewer may have:

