8. STUDY ASSESSMENTS AND PROCEDURES

| | Baseline | Day -5 to +14 or Discharge (Daily unless stated otherwise) | After Discharge: Weekly until stable | Day 30 | Day 100 | Every 3 – 6 months | 1 Year | Yearly until 5 years from transplant |
|---|----------|--|--------------------------------------|--------|---------|------------------------------|--------|--------------------------------------|
| H&P with VSS | X | X | X | X | X | X | X | X |
| Performance Status | X | X | X | X | X | X | X | X |
| AE Assess | | X | X | X | X | X | | |
| ECG, ECHO, and/or MUGA Scan, and/or Cardiac MRI | X | | | | | | X | yearly if abnormal |
| PFT's | X | | | | | | X | yearly if abnormal |
| CBC & Diff | X | X | X | X | X | X | X | X |
| PT/PTT/INR | X | | | | | | | |
| BMP, Mg, Phos | X | X | X | X | X | X | X | X |
| LFT's, LDH | X | Weekly | X | X | X | | X | X |
| TFT's (TSH, free T4) | X | | | | | | X | X |
| IgG | X | | | X | X | | X | |
| CD4, CD8 | | | | X | X | | X | |
| CT or MRI Primary / Metastatic Site | X | | | | X | X (at 6 months and 9 months) | X | X |
| PET Scan | X | | | | X | X (at 6 and 9 months) | X | X |

| | | | | | | | | |
|-----------------------------|---|--|--|--|--|--|---|--|
| Audiogram | X | | | | | | X | |
| Creatinine Clearance or GFR | X | | | | | | | |
| DEXA Scan | | | | | | | X | |

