15.4 Analysis of Safety Data

Safety analyses will be performed on all patients who receive any dose of study medication. Adverse events that occur more than 30 days after the administration of the last dose of treatment will not be included.

The safety and tolerability of study drug is determined by reported AEs, physical examinations, laboratory tests, and ECGs. All patients will be assessed regularly for potential occurrence of AEs from the time that treatment starts until 60 days after the last dose of study therapy. AEs will be summarized with the incidence and percentage of patients with at least one occurrence of a preferred term (according to the most severe NCI-CTCAE Version 4.0 grade) will be included. The number of AEs reported will also be summarized. Causality (relationship to study drug) will be summarized separately. Duration of AE will be determined and included in listings along with action taken and outcome. Laboratory AEs will be monitored from the time that treatment starts until 30 days after the last dose of study therapy. Laboratory results will be classified according to NCI-CTCAE, Version 4.0. Incidence of laboratory abnormalities will be summarized; laboratory results not corresponding to an NCI-CTCAE Version 4.0 term will not be graded. Laboratory toxicity shifts from baseline to worst grade will also be provided. The results from physical examination and vital sign measurement will be tabulated. Descriptive statistics will be provided as appropriate.

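### The 1-year hearing, lung and cardiac-function tests have no stated route into the safety analysis, so the Aim 3.2 toxicity conclusion would be essentially acute

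*Combined protocol and SAP*

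**What the plan says.** Toxicity is one of only two aims. Section 3.2 reads "To evaluate the toxicities associated with undergoing high dose conditioning using Etoposide, Carboplatin and Ifosfamide followed by autologous stem cell transplantation". Section 5.4 follows patients for up to 5 years from transplant.

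Section 15.4 defines how safety is judged: "The safety and tolerability of study drug is determined by reported AEs, physical examinations, laboratory tests, and ECGs". It then sets a limit: "Adverse events that occur more than 30 days after the administration of the last dose of treatment will not be included". The next paragraph has AEs assessed "from the time that treatment starts until 60 days after the last dose of study therapy", and ends laboratory AE monitoring at 30 days.

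The schedule in Section 8 gives these rows:

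- Cardiac tests, in one combined row ("ECG, ECHO, and/or MUGA Scan, and/or Cardiac MRI"), and lung function tests: baseline, 1 year, then each later year only where the result was abnormal.
- Audiogram: baseline and 1 year.
- Thyroid tests: baseline, 1 year and every year to 5 years.
- "Creatinine Clearance or GFR": baseline only.
- Metabolic panel (BMP): every column.
- AE assessment: every column from Day -5 through the 3- to 6-monthly visits; blank at baseline, 1 year and yearly.
- History and physical examination: every column.

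The risk lists in Section 5.5.6 include hearing ("Damage to organs which may cause hearing and balance problems"), heart failure or heart attack, fluid around the lungs, and kidney ("Kidney damage which may cause swelling, may require dialysis"). They list no thyroid risk.

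**The concern.** For hearing, lung and heart, the trial will hold a baseline and a 1-year result on organs that its own risk lists name. Nothing in Section 15 says that these pairs will be summarised.

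Take a patient whose audiogram is normal at entry and shows a loss at 1 year, with no earlier complaint. The audiogram is not a Section 15.4 measure, no AE assessment is scheduled at that visit, and an AE with that onset would be excluded by the 30-day rule. Unless the deficit is noted on physical examination, the patient can appear in the report with no hearing toxicity.

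The study has 10 patients, so a single late organ finding is a material part of the evidence for Aim 3.2. A toxicity statement that leaves such findings out describes the early period only, and a reader could take it as covering the whole follow-up.

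**Working it through.** The plan states no figure to reproduce. The check sets the Section 8 schedule against the measures and time limits in Section 15.4.

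**Step 1. Where the windows end.** The treatment table puts the last chemotherapy on Day -2.

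- 30-day limit: -2 + 30 = Day +28 (Day +30 if the Day 0 cell infusion counts as the last dose).
- 60-day limit: -2 + 60 = Day +58 (Day +60 on the same alternative).

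**Step 2. Where the visits fall.** Days after last chemotherapy = visit day + 2.

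| Visit | Days after last chemotherapy | Within 30 days | Within 60 days |
|---|---|---|---|
| Day 14 | 16 | yes | yes |
| Day 30 | 32 | no (yes if counted from Day 0) | yes |
| Day 100 | 102 | no | no |
| 1 year (Day 365) | 367 | no | no |

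The 1-year tests are 367 - 30 = 337 days past the 30-day limit and 367 - 60 = 307 days past the 60-day limit. Section 15.4's two windows conflict with each other, but settling that conflict either way would not bring in the 1-year results. The required collection of serious AEs in Section 12.6 also runs for 60 days.

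**Step 3. Each domain against Section 15.4.**

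| Domain | First scheduled test after baseline | Named in 15.4? | Other stated route |
|---|---|---|---|
| Hearing (audiogram) | 1 year | no | none for the test result |
| Lung function | 1 year | no | none for the test result |
| Heart: ECHO, MUGA, MRI | 1 year | no | none for the test result |
| Heart: ECG | 1 year | yes | no ECG table described |
| Thyroid | 1 year, then yearly | yes, as a laboratory test | laboratory shift table |
| Kidney: serum chemistry | daily from Day -5, then every column | yes, as a laboratory test | laboratory AEs and shift table |
| Kidney: clearance or GFR | not scheduled | no | none |

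Hearing, lung and cardiac function have no scheduled post-baseline measurement inside either AE window, and their test results appear in no analysis described in Section 15. ECG is a named measure, but it shares a row whose wording can be read as satisfied by another cardiac test.

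**Step 4. Would an AE assessment at 1 year be enough?** No. AE assessment is already scheduled at Day 100 and every 3 to 6 months, and events first arising by then are already beyond the 30-day exclusion. Marking the 1-year cell alone would collect events that Section 15.4 still drops.

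**The case against.** The best defence is that this is a 10-patient pilot sized by availability, that Aim 3.2 does not mention late effects, and that Section 15.4 openly confines AE analysis to the early period. On that view an acute-only conclusion misleads only if it is presented as something wider. It is also fair that late findings in patients with a second or later recurrence are hard to attribute: earlier chemotherapy and radiotherapy, and treatment given after relapse, can produce them, and a paired baseline does not remove this. Both points limit how late findings should be described. Neither explains scheduling the tests at 1 year and then giving them no place in the analysis.

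Three stronger readings are tempting, and the documents do not support them.

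- *Renal toxicity is missed.* The clearance row is marked at baseline only, but the metabolic panel is in every column, Section 5.5.4.4 calls for renal monitoring by institutional standard, and laboratory shifts from baseline to worst grade are reported. What is lost is a post-baseline clearance value.
- *Thyroid toxicity is missed in the same way.* Thyroid tests continue yearly to 5 years and are laboratory tests within Section 15.4. The sentence on laboratory shifts carries no time limit of its own, so late values can enter. Thyroid damage is also not a listed risk of the regimen.
- *The frequency bands in the risk lists measure the gap.* Applied to 10 patients, they give the chance that a case occurs, not the chance that it goes unreported.

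Clinically evident organ events in the early period also still enter, through AEs and physical examination. An overt deficit at 1 year could appear in the tabulated examination findings, which have no stated time limit.

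**Conclusion.** The point stands in a limited form. For hearing, lung function and cardiac function, the plan schedules a paired baseline and 1-year assessment and gives the results no stated route into the safety analysis. Three features act together: the tests are not named measures, AE assessment is blank at 1 year and yearly, and AEs after about Day +28 are excluded. The consequence is that late or subclinical toxicity in these three domains is left out and the Aim 3.2 conclusion is essentially acute. Renal and thyroid laboratory results are not in this position.

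This should be corrected. It does not invalidate the early safety analysis.

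The day counts assume that the last dose is the Day -2 chemotherapy and that 1 year is Day 365 after transplant; counting from Day 0 moves the limits by two days and changes nothing for the 1-year tests. The conclusion also takes Section 15.4's list of measures as complete. Its closing reference to descriptive statistics where suitable does not commit the sponsor to reporting these tests.

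**What to change.** 1. Add to Section 15.4 a descriptive late-toxicity table, for example: *Audiogram, lung function and cardiac function/ECG results will be tabulated per patient as baseline, 1-year value and change, graded by CTCAE v4.0 where a term exists, and reported as late toxicity separately from the acute AE tables. Thyroid function will be shown alongside as a descriptive late effect.* State how many of the treated patients have both measurements.
2. State in Section 15.4 that these late findings are exempt from the 30-day exclusion, and mark AE assessment at the 1-year and yearly visits. The mark has no effect on the results without the exemption. The same sentence should say whether AEs from the Day 100 and 3- to 6-monthly assessments are reported.
3. Optionally, report calculated creatinine clearance at the follow-up visits from the chemistry already scheduled, as change from baseline. This assumes that the metabolic panel includes creatinine; the documents do not list its components.

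The cost is a short addition to Section 15.4, a few marks in existing columns of the schedule, and a few more tables. No new visit, blood draw or procedure is needed, and treatment is unaffected. Because late findings cannot be fully separated from the effects of earlier chemotherapy and radiotherapy or of treatment after relapse, they should be presented without attribution to the regimen. If the sponsor prefers to keep the analysis acute, the report should say that its toxicity conclusion covers only the period analysed.

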5.3. Duration of Treatment

The subjects will be on treatment for approximately 3 months which includes the pre-treatment evaluations, the conditioning treatment, and 6-8 weeks of post treatment supportive care.

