| Treatment | Day - 5 | Day-4 | Day-3 | Day-2 | Day - 1 | Day 0 |
| Ifosfamide (2.5 g/m ² /day) IV over 17 hours for four days | X | X | X | X | | |
| Carboplatin (300 mg/m ² /day) IV over 3 hours for four days | X | X | X | X | | |
| Etoposide (300mg/m ² /day) IV over 3 hours for four days | X | X | X | X | | |
| Stem Cell Infusion (Minimum 48 of hours from last dose). | | | | | | X |

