12.6 SAE Reporting: All grade 3 non-hematologic SAE's must be collected, including those thought to be associated with protocol-specified procedures. Collection of all SAEs must continue for 60 days after the last administration of the investigational products. All SAE's must be reported to UF-IRB-01 within 5 working days.

12.7 Laboratory Test Abnormalities – all laboratory test results captured as part of the study should be recorded following institutional procedures. In general, non-clinically significant laboratory deviations are not considered adverse events. Laboratory deviations which require treatment delay, modification or discontinuation or are otherwise clinically significant should be reported as adverse events.

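### The 30-day laboratory window in 15.4 closes at about Day +28 (Day +30 at the latest), so it misses or only just reaches the Day 30 bloods and always misses Day 100

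*Combined protocol and SAP*

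**What the plan says.** Section 15.4 (Analysis of Safety Data) gives laboratory events their own limit: "Laboratory AEs will be monitored from the time that treatment starts until 30 days after the last dose of study therapy". An exclusion rule earlier in the section has the same length: "Adverse events that occur more than 30 days after the administration of the last dose of treatment will not be included". Between the two, adverse events in general are assessed "from the time that treatment starts until 60 days after the last dose of study therapy". Section 12.6 uses 60 days for serious events: "Collection of all SAEs must continue for 60 days after the last administration of the investigational products".

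The conditioning table in 5.5.4 has the columns "Day - 5 | Day-4 | Day-3 | Day-2 | Day - 1 | Day 0". Each drug is marked on the first four of these; the ifosfamide row reads "IV over 17 hours for four days | X | X | X | X". Cells are infused on Day 0. The infusion row sets a minimum interval from the last dose, so in that table the last dose means chemotherapy.

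The schedule in Section 8 runs on the transplant calendar. At both Day 30 and Day 100 it places blood counts, chemistry, liver tests, IgG, CD4/CD8 and an AE assessment. Section 5.3 says that subjects are on treatment for about three months, including "6-8 weeks of post treatment supportive care". Specific Aim 3.2 is to evaluate the toxicities of the regimen.

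**The concern.** The laboratory window counts from the last dose, whereas the visits count from transplant. Because dosing ends before transplant, a 30-day window ends just short of the Day 30 visit. It also ends inside the aftercare period that 5.3 treats as time on treatment.

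Toxicity is one of only two specific aims. Kidney damage, liver damage and pancytopenia are listed risks in 5.5.6. A laboratory abnormality that first appears, or worsens, after about Day +28 would be found at a scheduled visit and then left out of the laboratory AE summary. With 10 patients planned, each patient omitted from an incidence moves it by 1/10 = 10 percentage points.

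**Working it through.** The plan does not convert its 30 days into a transplant day, so there is no stated figure to reproduce. The check is calendar arithmetic.

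**Inputs**
- Last chemotherapy dose: Day -2 (conditioning table). The last 17-hour ifosfamide infusion could end on Day -1.
- Cell infusion: Day 0 (5.5.4.1.5 and the conditioning table).
- Window length: 30 days for laboratory AEs and for the exclusion rule (15.4); 60 days for AE assessment (15.4) and SAE collection (12.6).
- Visits: Day 30 and Day 100 (Section 8).
- Aftercare: 6 to 8 weeks = 42 to 56 days (5.3).

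**Closing day = anchor day + window length**

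| Anchor | 30-day window closes | Day 30 visit | Day 100 visit | 60-day window closes |
|---|---|---|---|---|
| Day -2, last dose | -2 + 30 = Day +28 | 2 days late | 72 days late | -2 + 60 = Day +58 |
| Day -1, infusion runs over | -1 + 30 = Day +29 | 1 day late | 71 days late | -1 + 60 = Day +59 |
| Day 0, cell infusion | 0 + 30 = Day +30 | on the boundary | 70 days late | 0 + 60 = Day +60 |

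Counted from Day -2, the Day 30 visit is 30 + 2 = 32 days after the last dose and the Day 100 visit is 100 + 2 = 102 days after it.

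**Against the aftercare period**
- Both counted from the last dose: 42 - 30 = 12 and 56 - 30 = 26, so the window ends 12 to 26 days before aftercare does.
- Aftercare counted from transplant, window closing on Day +28: 42 - 28 = 14 and 56 - 28 = 28, so 14 to 28 days before.
- With a 60-day window counted from the last dose, aftercare ends on Day +40 to +54, before Day +58. If aftercare is counted from transplant it ends on Day +42 to +56, also before Day +58.

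A 60-day window therefore takes in Day 30 and all of the aftercare. It still misses Day 100, by 100 - 58 = 42 days (40 on the Day 0 anchor).

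**Which outputs are affected**
- Laboratory AEs: explicit. The laboratory sentence and the exclusion sentence both stop at 30 days.
- Incidence of laboratory abnormalities and the worst-grade shift table: inferred. Both follow the laboratory sentence in 15.4 but have no window of their own.
- IgG: baseline, then Day 30 as the first later sample, so it depends wholly on how Day 30 is treated.
- CD4/CD8: first sampled at Day 30, with none at baseline, so no shift from baseline is possible under any window.

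**The case against.** The strongest reply is that little is really lost.

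- **The anchor is undefined.** Study therapy is not defined, and the regimen under study includes the transplant. On a Day 0 anchor the window closes on Day +30, and an on-time Day 30 visit is just inside. This stands as an alternative. The conditioning table's use of the term favours Day -2 without settling it.
- **No visit windows are given.** A Day 30 visit held on Day +28 counts even on the Day -2 anchor. A reader might infer that no patient would have an in-window IgG or CD4/CD8 result; that would need every visit to fall on its nominal day as well as the Day -2 anchor. Nor does the plan say that the 30 days were chosen to end with the Day 30 visit.
- **Sampling continues.** A reader might infer that laboratory monitoring stops while patients are on treatment. It does not: Section 8 continues blood tests for up to five years, and 12.7 makes clinically significant deviations reportable as AEs. The limit falls on what is analysed as a laboratory AE.
- **Early sampling is dense.** Counts and chemistry are daily to Day +14 or discharge, with liver tests weekly; after discharge all three are weekly until the patient is stable. Most delayed count recovery would be seen before Day +28, and a worst-grade table does not show time to recovery in any case. What is at risk is narrower: abnormalities that begin or worsen late.
- **The 30-versus-60-day conflict is the larger fault.** Settling it at 60 days would cover Day 30 and the aftercare, leaving Day 100 as the distinct issue. That is right, but the laboratory sentence has its own 30-day limit and would need changing too.
- **Day 100 is a preference.** No section promises laboratory toxicity analysis to Day 100. That is fair, and it makes the change an improvement to the analysis rather than the correction of a broken commitment. The case for it is that the plan already schedules bloods and AE assessment on that day.

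**Conclusion.** The point holds as a cheap improvement to a descriptive pilot. The laboratory AE window closes at about Day +28, or Day +30 on the most generous anchor. A Day 30 visit on its nominal day falls up to 2 days outside or exactly on the boundary. Day 100 is 70 to 72 days outside, on any reading. Counting both from the last dose, the window ends 12 to 26 days before the aftercare that 5.3 counts as treatment.

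This rests on Section 8 counting its days from transplant, as its Day -5 to +14 column implies, and on visits being held on their nominal days.

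The documents do not support the stronger reading that all Day 30 and Day 100 results are certain to drop out of every laboratory table. The exclusion is explicit for laboratory AEs only, and inferred for the incidence and shift tables. How many patients would have an abnormality that first appears or worsens after about Day +28 cannot be estimated from the documents. No efficacy result or decision rule depends on this; what changes is how completely Aim 3.2 is reported.

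**What to change.** In 15.4:

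1. Count the laboratory analysis window from transplant (Day 0). Start it at the beginning of conditioning and end it at the Day 100 visit.
2. State that this window applies to laboratory AEs, to the incidence of laboratory abnormalities and to the worst-grade shift table.
3. Align the 30-day exclusion sentence with it; otherwise late laboratory AEs are still removed. The 30-day and 60-day statements in 15.4 and 12.6 must be reconciled in the same edit.
4. List Day 30 and Day 100 grades separately for tests that have a CTCAE grade, so that unresolved abnormalities can be seen. Do not tabulate a baseline shift for CD4/CD8.

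At a minimum, give laboratory events the 60-day window already used for AE assessment in 15.4 and for SAEs in 12.6. It closes at about Day +58 and covers Day 30 and the 6 to 8 weeks of care, but not Day 100.

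The cost is a few sentences and slightly longer tables. Every sample is already scheduled. Reported toxicity may look somewhat less favourable, and later abnormalities may reflect relapse or subsequent therapy rather than the conditioning. The separate Day 30 and Day 100 listings help a reader to judge this.
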